8.1.2 Serious Adverse Events

Investigators should report AEs that meet the definition of an SAE (see Appendix 4 for definition).

8.1.3 Monitoring pregnancies for potential Serious Adverse Events

It is important to monitor the outcome of pregnancies of patients in order to provide SAE data on congenital anomalies or birth defects.

In the event that a patient or their partner becomes pregnant during the SAE reporting period please complete a Pregnancy Notification Form (providing the patient's details) and return to the trials office within 24 hours of becoming aware. If it is the patient who is pregnant provide outcome data on a follow-up Pregnancy Notification Form. Where the patient's partner is pregnant consent must first be obtained and the patient should be given a pregnancy release of information form to give to their partner. If the partner is happy to provide information on the outcome of their pregnancy they should sign the pregnancy release of information form. Once consent has been obtained provide details of the outcome of the pregnancy on a follow-up Pregnancy Notification Form. If appropriate also complete an SAE Form as detailed below.

8.1.4 Reporting period

Details of all AEs (except those listed above) will be documented and reported from the date of commencement of protocol defined treatment until 30 days after the administration of the last treatment (refer to Treatment Schedule A and B).

8.2 Reporting Procedure

8.2.1 Site

8.2.1.1 Adverse Events

AEs should be reported on an AE Form (and where applicable on an SAE Form). An AE Form should be completed at each visit and returned to the Trials Office.

AEs will be reviewed using the Common Terminology Criteria for Adverse Events (CTCAE), version 4.0 (see Appendix 5). Any AEs experienced by the patient but not included in the CTCAE should be graded by an Investigator and recorded on the AE Form using a scale of: (1) mild, (2) moderate or (3) severe. For each sign/symptom, the highest grade observed since the last visit should be recorded.

8.2.1.2 Adverse Events of Special Interest (AESI) Ibrutinib

The following list of specific adverse events will be assessed as part of standard safety monitoring activities by Pharmacocyclics. These events should be reported to the trial office as SAEs within 24 hours of awareness following the procedure detailed in section 8.2.1.3. All events of special interest should be submitted on the SAE form within 24 hours of awareness even if they do not meet serious criteria.

Major Haemorrhage

In order for an event to qualify as a major haemorrhage, it must include ANY one of the following criteria:

- Any treatment-emergent haemorrhagic adverse event of Grade 3 or higher. All haemorrhagic events requiring a transfusion of red blood cells should be reported as Grade 3 or higher per CTCAE.
- Any treatment emergent serious adverse event of bleeding of any grade.
- Any treatment emergent central nervous system haemorrhage/hematoma of any grade.
- This definition is the recommendation provided by the Subcommittee on Control of Anticoagulation of the Scientific and standardisation Committee of the International Society on Thrombosis and haemostasis (Schulman 2005).

Intracranial Haemorrhage

Any intracranial haemorrhage adverse event, including subdural hematoma/haemorrhage, epidural haematoma/haemorrhage and intracerebral haemorrhage, of any grade severity.

8.2.1.3 Adverse Events of Special Interest (AESI) Obinutuzumab

The following types of events are considered by the Sponsor to be "AEs of special interest" (AESIs) due to their observed frequency and/or clinical relevance:

- AEs associated with obinutuzumab infusion (defined as any AE considered as related to obinutuzumab occurring during or within 24 hours of an obinutuzumab infusion and meets the seriousness criteria
- Infections fulfilling the criteria of seriousness
- Neutropenia fulfilling the criteria of seriousness
- Tumour Lysis Syndrome

8.2.1.4 Other Malignancies

In addition to all routine AE reporting, all new malignant tumours including solid tumours, skin malignancies and haematological malignancies are to be reported for the duration of study treatment and during the specified follow-up period.

8.2.1.5 Serious Adverse Events

For more detailed instructions on SAE reporting refer to the SAE Form Completion Guidelines contained in the Investigator Site File (ISF).

AEs defined as serious and which require reporting as an SAE should be reported on an SAE Form.

When completing the form, the Investigator will be asked to define the causality and the severity of the AE which should be documented using the CTCAE version 4.03.

On becoming aware that a patient has experienced an SAE, the Investigator (or delegate) must complete, date and sign an SAE Form. The form should be sent to the Trials Office using the contact details listed below as soon as possible and no later than 24 hours after first becoming aware of the event:

To report an SAE email the SAE Form to:

[contact] and CC [contact]

On receipt the Trials Office will allocate each SAE a unique reference number. This number will be sent back to the site as proof of receipt. If confirmation of receipt is not received within 1 working day please contact the Trials Office. The SAE reference number should be quoted on all correspondence and follow-up reports regarding the SAE.

For SAE Forms completed by someone other than the Investigator the Investigator will be required to countersign the original SAE Form to confirm agreement with the causality and severity assessments. The form should then be returned to the Trials Office in the post and a copy kept in the ISF.

Investigators should also report SAEs to their own Trust in accordance with local practice.

8.2.1.6 Provision of follow-up information

Patients should be followed up until resolution or stabilisation of the event. Follow-up information should be provided on a new SAE Form (refer to the SAE Form Completion Guidelines for further information).

8.2.2 Trials Office

On receipt of an SAE form seriousness and causality will be determined independently by a Clinical Coordinator. An SAE judged by the Investigator or Clinical Coordinator to have a reasonable causal relationship with the trial medication will be regarded as a Serious Adverse Reaction (SAR). The Clinical Coordinator will also assess all SARs for expectedness. If the event meets the definition of a SAR that is unexpected (i.e. is not defined in the Reference Safety Information) it will be classified as a Suspected Unexpected Serious Adverse Reaction (SUSAR).

8.2.3 Reporting to the Competent Authority and main Research Ethics Committee

8.2.3.1 Suspected Unexpected Serious Adverse Reactions

The Trials Office will report a minimal data set of all individual events categorised as a fatal or life threatening SUSAR to the Medicines and Healthcare products Regulatory Agency (MHRA) and main Research Ethics Committee (REC) within 7 days. Detailed follow-up information will be provided within an additional 8 days.

All other events categorised as SUSARs will be reported within 15 days.

8.2.3.2 Serious Adverse Reactions

The Trials Office will report details of all SARs (including SUSARs) to the MHRA and main REC annually from the date of the Clinical Trial Authorisation, in the form of a Development Safety Update Report (DSUR).

8.2.3.3 Adverse Events

Details of all AEs will be reported to the MHRA on request.

8.2.3.4 Other safety issues identified during the course of the trial

The MHRA and main REC will be notified immediately if a significant safety issue is identified during the course of the trial.

8.2.4 Investigators

Details of all SUSARs and any other safety issue which arises during the course of the trial will be reported to Principal Investigators. A copy of any such correspondence should be filed in the ISF.

8.2.5 Data Monitoring Committee

The independent Data Monitoring Committee (DMC) will review all SAEs.

8.2.6 Manufacturer of Investigational Medicinal Product

All SAEs will be reported to the manufacturer of the Investigational Medicinal Products as guidelines set out in the research grant and supply agreement.

9. DATA HANDLING AND RECORD KEEPING

9.1 Data Collection

The Case Report Form (CRF) will comprise a set of forms capturing details of eligibility, baseline characteristics, treatment and outcome details etc., and will be provided to the Site at the time of initiation.

The CRF must be completed, signed/dated and returned to the Trials Office by the Investigator or an authorised member of the site research team (as delegated on the Site Signature and Delegation Log) within the timeframe specified into the CRF completion guidelines. The exceptions to this are the SAE Form and Withdrawal Form which must be co-signed by the Investigator.

Entries on the CRF should be made in ballpoint pen, in blue or black ink, and must be legible. Any errors should be crossed out with a single stroke, the correction inserted and the change initialled and dated. If it is not obvious why a change has been made, an explanation should be written next to the change.

Data reported on each form should be consistent with the source data or the discrepancies should be explained. If information is not known, this must be clearly indicated on the form. Missing and ambiguous data will be queried. All sections are to be completed before returning. Quality of Life questionnaires do not require recording on the CRF and should be forwarded to the Trials Office upon completion.

In all cases it remains the responsibility of the Investigator to ensure that the CRF has been completed correctly and that the data are accurate.

The completed originals should be sent to the Trials Office and a copy filed in the Investigator Site File. Trial forms may be amended by the Trials Office, as appropriate, throughout the duration of the trial. Whilst this will not constitute a protocol amendment, new versions of the form must be implemented by participating sites immediately on receipt.

9.2 Archiving

It is the responsibility of the Principle Investigator to ensure all essential trial documentation and source records (e.g. signed Informed Consent Forms, Investigator Site Files, Pharmacy Files, patients' hospital notes, copies of CRFs etc.) at their site are securely retained for at least 10 years after the end of the trial or following the processing of all biological material collected for research, whichever is the later. Do not destroy any documents without prior approval from the CRCTU Document Storage Manager.

10. QUALITY MANAGEMENT

10.1 Site Set-up and Initiation

All sites will be required to sign a Clinical Study Site Agreement prior to participation. In addition all participating Investigators will be asked to sign the necessary agreements, registration forms and supply a current CV to the Trials Office. All members of the site research team will also be required to sign the Site Signature and Delegation Log, which should be returned to the Trials Office. Prior to commencing recruitment all sites will undergo a process of initiation. Key members of the site research team will be required to attend either a meeting or a teleconference covering aspects of the trial design, protocol procedures, Adverse Event reporting, collection and reporting of data and record keeping. Sites will be provided with an Investigator Site File and a Pharmacy File containing essential documentation, instructions, and other documentation required for the conduct of the trial. The Trials Office must be informed immediately of any change in the site research team.

10.2 On-site Monitoring

Monitoring will be carried out as required following a risk assessment and as documented in the CRCTU Quality Management Plan. Additional on-site monitoring visits may be triggered for example by poor CRF return, poor data quality, low SAE reporting rates, excessive number of patient withdrawals or deviations. If a monitoring visit is required the Trials Office will contact the site to arrange a date for the proposed visit and will provide the site with written confirmation. Investigators will allow the IcICLLe trial staff access to source documents as requested.

10.3 Central Monitoring

Where a patient has given explicit consent sites are requested to send in copies of signed Informed Consent Forms for in-house review.

Trials staff will be in regular contact with the site research team to check on progress and address any queries that they may have. Trials staff will check incoming Case Report Forms for compliance with the protocol, data consistency, missing data and timing. Sites will be sent Data Clarification Forms requesting missing data or clarification of inconsistencies or discrepancies.

Sites may be suspended from further recruitment in the event of serious and persistent non-compliance with the protocol and/or GCP, and/or poor recruitment. Any major problems identified during monitoring may be reported to the Trial Management Group and Data Monitoring Committee and the relevant regulatory bodies. This includes reporting serious breaches of GCP and/or the trial protocol to the main Research Ethics Committee (REC) and the Medicines for Healthcare products Regulatory Agency (MHRA).

10.4 Audit and Inspection

The Investigator will permit trial-related monitoring, audits, ethical review, and regulatory inspection(s) at their site, providing direct access to source data/documents.

Sites are also requested to notify the Trials Office of any MHRA inspections.

10.5 Notification of Serious Breaches

In accordance with Regulation 29A of the Medicines for Human Use (Clinical Trials) Regulations 2004 and its amendments the Sponsor of the trial is responsible for notifying the licensing authority in writing of any serious breach of:

- The conditions and principles of GCP in connection with that trial or;
- The protocol relating to that trial, within 7 days of becoming aware of that breach

For the purposes of this regulation, a “serious breach” is a breach which is likely to effect to a significant degree:

- The safety or physical or mental integrity of the subjects of the trial; or
- The scientific value of the trial

Sites are therefore requested to notify the Trials Office of a suspected trial-related serious breach of GCP and/or the trial protocol. Where the Trials Office is investigating whether or not a serious breach has occurred sites are also requested to cooperate with the Trials Office in providing sufficient information to report the breach to the MHRA where required and in undertaking any corrective and/or preventive action.

11. END OF TRIAL DEFINITION

The trial end date is deemed to be 6 months after the last patient has completed the protocol defined interventional treatment. This will allow sufficient time for the completion of protocol procedures, data collection and data input.

The Trials Office will notify the MHRA and REC that the trial has ended at the appropriate time and will provide them with a summary of the clinical trial report within 12 months of the end of trial.

Sites should continue to notify the Trials Office of changes in Principal Investigator by completing and returning (where required) an Investigator Registration Form together with a current signed and dated CV until otherwise notified.

12. STATISTICAL CONSIDERATIONS

12.1 Definition of Outcome Measures

12.1.1 Primary Objectives / Outcome Measures

- Proportion of patients achieving MRD-negative remission by IWCLL criteria (depletion of CLL below 0.01% in the peripheral blood and bone marrow) in a) the initial phase of the study at or before the 6 month assessment and b) the Extension Study at or before the 9 month assessment. Independent decisions will be made for each study (initial and extension).

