Participants will be recruited from TAP centres with expertise in the diagnosis and treatment of CLL. It is envisaged that all eligible patients at these centres will be offered the opportunity to participate in the study.

Assessment of response

Assessment of MRD will be carried out on peripheral blood samples throughout the study. It will be measured by flow and assessed using current IWCLL guidelines (refer to Appendix 1 for these guidelines and references). Assessment of MRD in bone marrow will be carried out on monotherapy patients after 6 months of continuous treatment with ibrutinib, and for combination therapy patients at 9 months (3 months after completion of combination therapy to allow for washout of antibodies). This is in line with comparable studies and IWCLL guidelines on assessment of MRD; that is to say that response should be assessed 2 months after the treatment has finished. Whilst extension study patients will continue on ibrutinib monotherapy after the 6 cycles of obinutuzumab, the effect of any synergy between ibrutinib and obinutuzumab should be evaluated after cessation of the second IMP. We can thus determine if administration of the combination therapy leads to a sustained response in patients when examining MRD in both peripheral blood at 1, 3, 6 and 9 months and bone marrow at 1 and 9 months.

Biological response will be assessed by way of peripheral blood and/or bone marrow examinations taken over a 12 month period. Further samples will also be collected every 6 months after this date, and 6 months after the patients achieve a clinical complete or MRD negative remission. If patients become confirmed MRD negative they will also stop treatment.

The key biological end-points will be complete following 6 months of trial treatment with secondary end-points of Modified IWCLL Response Criteria continuing to 12 months and beyond if patients continue to respond.

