7.1.2 Obinutuzumab treatment

In patients who are ibrutinib naïve, ibrutinib 420mg/day should be started on Day 0 (24 hours before commencing obinutuzumab) to help reduce potential infusion reactions.

For monitoring of certain AEs, such as TLS, the results of the local haematology and biochemistry should be assessed by a delegated Investigator prior to subsequent infusion.

The most frequently observed AE in patients receiving obinutuzumab were IRRs which occurred predominantly during infusion of the first 1000 mg. In order to mitigate this, **appropriate premedication must be given (see Section 7.6.2).**

Dose modifications and delays for obinutuzumab are detailed in Section 7.4.2. Precautions for use are detailed in Section 7.9.

The initial dose of obinutuzumab should be split in accordance with the scheduled stipulated below (see also Table 1):

Cycle 1

Two infusion bags should be prepared for the infusion on Days 1 and 2 (100 mg for Day 1 and 900 mg for Day 2).. These will then be given as follows:

Day 1: 100 mg obinutuzumab intravenous infusion

- Administered at 25 mg per hour over 4 hours
- For the first dose given on day 1, if the first dose is completed without modifications of the infusion rate or interruptions, the second dose can be administered on the same day (as specified in Day 1 (continued) in Table 1 below)
- Appropriate time, conditions and medical supervision should be available throughout the infusion
- If there are any modifications of the infusion rate or interruptions during the first 100 mg the second dose must be administered the following day

Day 2: 900 mg obinutuzumab intravenous infusion (if not previously given on day 1)

- Administered at 50 mg per hour. In the absence of any infusion related reactions or hypersensitivity, the rate of infusion may be escalated in increments of 50 mg per hour every 30 minutes to a maximum rate of 400 mg per hour

Days 8 and 15: 1000 mg Obinutuzumab intravenous infusion

- Infusions may start at a rate of 100mg per hour and increase by 100mg/hr increments every 30 minutes to a maximum rate of 400mg per hour

Cycles 2-6

Days 29, 57, 85, 113 and 141

- All subsequent cycles will consist of one dose on the first day of the 28 day cycle

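### The extension primary endpoint admits samples taken before antibody washout, contrary to section 3's reason for Month 9, and section 7.2.3 does not settle which samples count

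*Protocol*

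**What the plan says.** Section 12.1.1 defines response as "depletion of CLL below 0.01% in the peripheral blood and bone marrow", counted in "b) the Extension Study at or before the 9 month assessment". Section 2.2 and the synopsis match it.

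Section 3 explains the timing. Marrow MRD is assessed "for combination therapy patients at 9 months (3 months after completion of combination therapy to allow for washout of antibodies". The section cites the principle that "response should be assessed 2 months after the treatment has finished" and adds that "the effect of any synergy between ibrutinib and obinutuzumab should be evaluated after cessation of the second IMP". It concludes: "We can thus determine if administration of the combination therapy leads to a sustained response in patients", by "examining MRD in both peripheral blood at 1, 3, 6 and 9 months and bone marrow at 1 and 9 months". Section 12.4 describes the extension primary outcome as assessed at 9 months of treatment.

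Section 12.2.2 sends the exact definition of MRD-negative to 7.2.3. That section asks for three successive negative bloods three months apart, with a marrow at the third. Section 7.2.3.1 points back to those time points. Its own requirement, however, is later blood and marrow within six months of the first negative blood, and it dates negativity at that first blood.

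Section 7.1.2 puts the obinutuzumab infusions of cycles 2 to 6 on "Days 29, 57, 85, 113 and 141".

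**The concern.** The endpoint wording and the reason for the assessment time describe two different outcomes: negative at some point up to Month 9, and negative at Month 9 after washout. The first can credit clearance that exists only while the antibody is present. Section 3 says the combination should be judged by the second.

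This one outcome drives the decision in 12.2.2 on whether the regimen goes forward. On 12.1.1 read literally, earlier samples can only add responders, so any error runs towards approval. The question of sustained response would also go unanswered, because a patient who has lost negativity by Month 9 is not separated from one who has kept it.

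**Working it through.** **Inputs.** Last planned infusion Day 141 (7.1.2); end of cycle 6 Day 168 (28-day cycles). Extension central blood on Days 8 and 15 and at Months 1, 3, 6 and 9; marrow at Months 1 and 9 (3, 7.2.2). Decision rule (12.2.2): Beta(1,1) prior, approve if the posterior probability that the rate exceeds 20% is at least 50%. One month is taken as 30.44 days.

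**1. Timing against the two-month principle (about 61 days).**
- Months 1 and 3 fall before Day 141, so they are on treatment.
- Month 6 is about Day 183: 183 − 141 = 42 days after the last infusion, and 183 − 168 = 15 days after cycle 6 ends. Adding the 7-day visit window to the 42 days gives 49.
- Month 9 is about Day 274: 274 − 141 = 133 days, or 4.4 months.

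Every scheduled sample before Month 9 falls short of two months.

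**2. Timing under the three-blood rule of 7.2.3.** The confirming marrow comes six months after the first negative blood.
- First negative Day 8: marrow at Month 6.3, which is 1.6 months after Day 141.
- First negative Month 1: marrow at Month 7.0, 2.4 months after.
- First negative Month 3: marrow at Month 9.0, 4.4 months after.

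Without cycle delays this marrow is never taken during obinutuzumab, but it can precede the washout that section 3 wants.

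**3. The definitions side by side.**

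| Patient | 12.1.1 literally | 7.2.3.1 | 7.2.3 three-blood rule | Negative at Month 9 |
|---|---|---|---|---|
| Blood negative Day 8; blood and marrow negative Month 1; positive from Month 3 | Responder | Can qualify | Not a responder | No |
| Blood negative Day 8, Month 3.3 and Month 6.3, marrow negative at Month 6.3; both positive Month 9 | Responder | Responder | Responder | No |
| Blood and marrow first negative at Month 9 | Responder | Awaits confirmation, dated Month 9 | Not confirmable until Month 15 | Yes |

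The definitions disagree on the first and third patients. None rejects the second for being positive at Month 9.

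**4. Who is exposed.** The only scheduled marrow during obinutuzumab is Month 1. Section 7.2.2 exempts roll-over patients from it (the Schedule B footnote exempts only those with a marrow in the previous 3 months). The on-antibody route therefore runs mainly through cohort (B)ii, which has at least 20 of at most 40 patients (12.5.2).

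**5. The decision rule.** P(θ > 0.2) under Beta(1+r, 1+n−r) reproduces Table 8 of section 12.2.2: 8/40 gives 56.19%, 7/40 gives 40.69%, 7/37 gives 50.03%, 6/35 gives 40.07%. For 30 to 40 patients, approval is 90.6–95.6% at a true rate of 30% and 3.2–9.4% at 10%, as the protocol states. With n = 40 the rule is to approve if r ≥ 8.

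**6. Illustration.** Assume a 10% post-washout rate and a share e of patients negative only before washout. P(approve) = P(X ≥ 8), X ~ Bin(40, 0.10 + e); for n = 30 the threshold is 6.

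| e | n = 40 | n = 30 |
|---|---|---|
| 0 | 4.2% | 7.3% |
| 2.5 points | 11.9% | 16.4% |
| 5 points | 24.4% | 28.9% |
| 7.5 points | 40.1% | 43.2% |
| 10 points | 56.3% | 57.3% |

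In 40 patients, 2.5 points is one patient (0.025 × 40). At a 30% post-washout rate the effect is small: 94.5% becomes 97.3% with 2.5 points.

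**The case against.** The strongest answer is that 12.2.2 makes 7.2.3 the operative definition. Three negative bloods three months apart, with marrow at the third, fit the extension visits at Months 3, 6 and 9. On that reading the Month 9 limit only bounds the window. A patient negative at Month 1 and positive afterwards is excluded. So is one with negative blood at Month 3, negative marrow at Month 9 and positive blood at Month 9. Section 7.2.3.1 also refers back to the 7.2.3 time points, so it could be read as adding nothing weaker. The washout phrase in section 3 concerns marrow; blood is deliberately tested throughout.

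Much of this stands. A reader might infer that every transient on-antibody clearance makes a responder, or that 7.2.3 is a separate matter. The documents support neither, given the cross-reference and the three-blood rule. What survives is that 7.2.3.1 states its own, looser condition, which negative blood on Day 8 or 15 followed by negative Month 1 blood and marrow can meet entirely during obinutuzumab. The three-blood rule itself can confirm before two months have passed, and neither rule asks for negativity at Month 9.

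It is also fair that one patient would tip a threshold rule under any endpoint, and that rapid clearance of blood lymphocytosis (1.2.3) is not the same as marrow below 0.01%.

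**Conclusion.** The point holds as an inconsistency in the endpoint definition. Sections 12.1.1, 2.2 and the synopsis conflict with sections 3 and 12.4, and the reference to 7.2.3 does not resolve the conflict because 7.2.3 and 7.2.3.1 differ.

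The direction of any error, on 12.1.1 read literally, is towards approval. Its size is unknown: the documents give no rate of early-only negativity, and the 4.2%, 11.9% and 24.4% rest on an assumed 10% post-washout rate and assumed early-only shares. A reader might conclude that the Bayesian rule is miscalibrated or that approval is known to be inflated. Neither follows: the rule's stated figures reproduce, and they describe whatever outcome is fed into it. The definition should be settled because the decision can turn on one patient in 40 (40.69% reject, 56.19% approve).

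**What to change.** For the extension primary analysis, define a responder as blood and marrow both below 0.01% in the samples of the Month 9 assessment (± 7 days, the visit window in 7.2). Count patients negative only earlier as non-responders. Report MRD negativity at any time up to Month 9 as a secondary outcome.

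Align 12.1.1, 2.2 and the synopsis. Amend 12.2.2 for the extension so that 7.2.3 and 7.2.3.1 govern only treatment stopping and not the endpoint; those treatment rules are left untouched here.

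The cost is wording, since Month 9 blood and marrow are already scheduled for both extension cohorts. The response proportion may be slightly lower. The analysis would also no longer call on the three-blood confirmation, so a patient first negative at Month 9 would count, which agrees with the present Month 9 limit.
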